### **3.3 Randomization and Blinding**

The study is an open-label, non-controlled, clinical trial. There is no randomization of patients or blinding.

### **3.4 Sample Size Justification**

No formal sample size calculation was made as no formal hypothesis testing will be performed. The sample size of 24 subjects in 4 cohorts is considered appropriate for a study of this type and was determined by practical considerations. Approximately 48 subjects will be screened to ensure that 24 subjects are enrolled into this study.

#### 4.0 STATISTICAL CONSIDERATIONS

Statistical analyses will be performed using SAS software, version 9.3 or higher. The safety population will be used as the analysis population for the primary endpoints and all safety end points. Full analysis set and per protocol set will be used as the analysis population for secondary and exploratory efficacy endpoints.

Continuous data will be summarized using n, mean, median, standard deviation (SD), minimum value, maximum value, 95% confidence interval (CI) and, if appropriate, number of missing values. Unless noted otherwise, summaries will be produced by visit (where applicable) and cohort. Summaries by visit will be based on nominal reporting. If more than one value is reported at a scheduled visit, the value collected closest to the intended visit date will be used. In the case of a tie, the latest version will be summarized.

Categorical data will be summarized using n, percentages. Percentages will be calculated based on the number of non-missing values. The number of missing values will be presented as a separate category with no percentage, if 1 or more patients are missing data for the summary. Otherwise, all categories will be presented (even if no patients are counted in the category). Counts of zero in any category will be presented with percentage as (0%).

Precision of summary statistics:

- Integer – Sample size (n, N) and number of missing responses (if displayed).
- One additional decimal place than reported/collected on the case report form (CRF) – mean, median, confidence interval.
- Two additional decimal places than reported/collected on the CRF – standard deviation.
- Same number of decimal places as reported/collected on the CRF – minimum, maximum.
- Percentages – one decimal place.

All data will be presented on listings in order of dosing cohort, patient, assessment date/time and assessment (in order collected on eCRF, unless specified otherwise). For display purposes, cohort labels will be ordered from smallest to largest. Dates will be presented in the format DDMMYY. Times will be displayed in 24-hour clock format. Numbering of tables, figures and listings will follow ICH E3 guidelines.

Unscheduled measurements will be excluded from the descriptive statistical analysis. However, unscheduled measurements that were performed immediately after the scheduled measurement, in case of a previous measurement error (e.g. equipment failure), will not be excluded from the analysis. In these cases, the original erroneous measurement will be excluded from the analysis and the unscheduled visit substituted. All the unscheduled measurements will be included in the listing.

Unless otherwise stated, the baseline value is defined as the as the last assessment result collected prior to the first dose of study medication.

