9.2 Clinical Laboratory Tests

Samples will be obtained for the clinical laboratory tests as defined in [Appendix H](#) outlined in the Schedule of Assessments ([Section 11](#)) at screening, at specified times during the study.

A certified central laboratory will be utilized to process and provide results for the clinical laboratory tests. The baseline laboratory test results for clinical assessment for a particular test will be defined as the last measurement prior to the initial dose of study drug.

For any laboratory test value outside the reference range that the investigator considers clinically significant, the investigator will:

- Repeat the test to verify the out-of-range value.
- Follow the out-of-range value to a satisfactory clinical resolution.
- Record as an AE any laboratory test value that (1) is confirmed and the investigator considers clinically significant; or (2) that requires a subject to be discontinued from the study; or (3) that requires a subject to receive treatment.

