12.5.2 Clinical Laboratory Tests

Descriptive statistics, including change from baseline, for the actual values of laboratory parameters will be presented for all scheduled time points by dose level. For subject data listings, abnormal values outside normal ranges will be flagged.

If data permits, urinalysis (pH and specific gravity) will be summarized (mean, SD, median, minimum, maximum, and n) at each time point.

Shift tables for laboratory parameters will be generated based on changes in National Cancer Institute Common Terminology Criteria for Adverse Events grade from baseline to worst postbaseline value. Graphical displays of key safety parameters, such as scatter plots of baseline versus worst postbaseline values, may be generated to better understand the study drug safety profile.

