#### **6.7.1.4 Clinical laboratory tests**

Descriptive statistics (mean, standard deviation [SD], minimum, maximum, and n), including change from baseline (pre-dose value of the relevant treatment period) for laboratory parameters of hematology, serum chemistry, coagulation, and urinalysis will be presented for all scheduled time points by cohort. Laboratory test results will be listed and abnormal values outside normal ranges will be flagged.

If data permits, urinalysis (pH and specific gravity) will be summarized (mean, SD, median, minimum, maximum, and n) at each time point. Shift tables for laboratory parameters will be generated based on changes in National Cancer Institute Common Terminology Criteria for AE grade from baseline to worst post-baseline value.

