## 7.0 HANDLING OF MISSING VALUES AND OUTLIERS

All available safety and efficacy data will be included in data listings and tabulations. No imputation of values for missing data will be performed.

When laboratory test results are above or below the limit of quantification (i.e proceeded by a “<” or “>” sign, for example “<xx”), the numerical value, xx, will be used for calculation in summary tables.

Missing or partially date missing for AEs/TEAE:

if due to partial dates or times it is not possible to definitively conclude that an AE is not treatment emergent, then a conservative approach will be taken whereby it will be classified as a TEAE e.g. if the first dose of study drug is “13May” and the AE starts in “May”, then that AE will be classified as a TEAE, unless the AE stop date precludes this (i.e. the AE stop date is definitively prior to the first dose of study drug).

Missing or partially missing medication date and Prior or Concomitant Medication (CM) determination:

If due to partial dates it is not possible to categorize a medication as prior or concomitant, then a conservative approach will be taken whereby it will be classified as such e.g. if the first dose of study drug is “13May” and another medication is started in “May”, then that medication will be classified as both previous and concomitant, unless the medication stop date precludes one of these classifications.

Missing safety data will not be replaced, except for AE and CM dates as described above.

Adverse events with missing severity will be summarized as severe. Adverse events with missing causal relationship will be summarized as related.

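### SAP 4.0 drops unscheduled measurements and does not exempt the laboratory shift table to worst post-baseline grade, so that table could miss a subject's worst value

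*SAP*

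**What the plan says.** SAP 4.0 (Statistical Considerations) sets a general rule: "Unscheduled measurements will be excluded from the descriptive statistical analysis". It makes one exception, for a repeat taken straight after a scheduled measurement that went wrong, and adds: "All the unscheduled measurements will be included in the listing". The rule names no type of table. It follows the visit conventions of the same section, among them "Summaries by visit will be based on nominal reporting".

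SAP 6.7.1.4 plans two kinds of laboratory summary. One is descriptive statistics at scheduled time points by cohort. The other, in its own sentence, is a shift table of Common Terminology Criteria (CTCAE) grade, "grade from baseline to worst post-baseline value". Nothing there says which draws feed the second.

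Protocol 12.5.2 has the same split. The descriptive statistics "will be presented for all scheduled time points by dose level"; the shift table, "grade from baseline to worst postbaseline value", carries no such limit.

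SAP 7.0 says: "All available safety and efficacy data will be included in data listings and tabulations". Protocol 12.6 has the same sentence. SAP 9.0, which records changes from the protocol, does not mention the exclusion.

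**The concern.** Safety is the primary objective, and SAP 6.7.1 counts laboratory tests among the primary safety endpoints. The study is wholly descriptive, so a rule about the descriptive analysis, read literally, reaches every table, including one meant to show each subject's worst laboratory grade. A by-visit mean needs one value per nominal visit, and leaving out off-schedule values is normal there. A worst-value table exists to catch the extreme, and there the same exclusion works against the purpose.

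Off-schedule values are foreseen. For an out-of-range result judged clinically significant, Protocol 9.2 tells the investigator: "Repeat the test to verify the out-of-range value". The value is then followed to resolution, and Protocol 9.9.4 allows further tests to monitor an adverse event. A verification or follow-up draw is not a measurement-error repeat, so the exception in SAP 4.0 does not cover it.

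The text also supports a narrower scope, so two programmers could each defend a different table.

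**Working it through.** The plan gives no figure to reproduce: it has no hypothesis test and no sample-size calculation. The checks are counts.

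**1. Scheduled laboratory draws.** Protocol 11.1, 11.2.5, 11.3, 11.4 and 11.7 place them at screening, 24 hours, Week 1, Week 2 and Week 13: 5 draws, 4 of them post-dose. The blood-volume table in Protocol 11.16 agrees: 15 mL of hematology / 3 mL per sample = 5 samples. Early termination before Week 13 uses the Week 13 procedures (11.13), so the post-dose maximum stays at 4. Early termination after Week 13 uses the end-of-study procedures (11.14), which include no laboratory tests.

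**2. Gaps.** Week 2 to Week 13 is 13 - 2 = 11 weeks. Week 13 to Week 104 is 104 - 13 = 91 weeks. Apart from an early-termination draw before Week 13, neither interval contains a scheduled laboratory test. A toxicity that arises and resolves in the first interval, or arises in the second, could be seen only at an unscheduled draw.

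**3. Direction, baseline fixed.** Take grades 0 to 4, four scheduled post-dose values and one unscheduled value: 5^5 = 3125 patterns. Dropping the unscheduled value lowers the maximum only when it exceeds all four scheduled values. That happens in 0 + 1^4 + 2^4 + 3^4 + 4^4 = 354 patterns. The maximum is unchanged in 3125 - 354 = 2771 and never higher. These are pattern counts, not probabilities.

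**4. Direction, baseline not fixed.** Screening is the only scheduled pre-dose laboratory draw, so a pre-dose repeat is unscheduled. Suppose the exclusion removed that repeat too. Over screening grade, repeat grade and worst grade there are 5^3 = 125 patterns. The shift is overstated when the repeat is above screening (10 pairs x 5 = 50), understated when it is below (50), and unchanged when they are equal (25). The shift can therefore move either way.

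**5. Size of one reclassification (grades assumed).** A subject has scheduled grades 0, 0, 1, 0 and one unscheduled grade 3.
- Exclusion applied to the shift table: max(0, 0, 1, 0) = 1.
- Exclusion limited to by-visit summaries: max(0, 0, 1, 0, 3) = 3.

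The subject moves from one cell to another. Each cell changes by 1/6 = 16.7 percentage points in a cohort of 6, or 1/24 = 4.2 points if an all-subject column is shown.

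**6. Frequency (assumed).** Let q be the chance that a subject's worst grade is seen only at an unscheduled draw, the same for all subjects and independent between them. The chance that at least one subject is affected is 1 - (1 - q)^n. The documents give no q; the table only shows the range.

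| q | n = 6 | n = 24 |
|---|---|---|
| 2% | 11.4% | 38.4% |
| 5% | 26.5% | 70.8% |
| 10% | 46.9% | 92.0% |
| 20% | 73.8% | 99.5% |

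**The case against.** The strongest reply is that the exclusion was never meant for this table. It sits directly after the nominal-visit rules. SAP 6.7.1.4 ties scheduled time points to the descriptive statistics and gives the shift table a separate sentence, as Protocol 12.5.2 does. SAP 7.0 sends all available safety data to tabulations. This reading is reasonable and may be the intended one. But SAP 4.0 does not say it: the rule is general and its one exception is something else. The support from SAP 7.0 and Protocol 12.6 is also weaker than it looks, because both sentences sit in sections on missing data.

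Second, many unscheduled draws would cost nothing. A repeat of an abnormal scheduled value that is no worse leaves the maximum alone. That stands. The loss is confined to a value that worsens after a scheduled draw, or first appears off schedule, and exceeds every scheduled grade.

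Third, the signal survives elsewhere. Unscheduled values are listed, and out-of-range results are flagged in the listings. Under Protocol 9.2, a value becomes an adverse event if it is confirmed and clinically significant, or if it leads to discontinuation or treatment. This stands as a limit on the harm. It is not a full substitute: adverse events are graded mild, moderate or severe (Protocol 9.9.1), and the shift table is the only planned laboratory summary by CTCAE grade.

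A reader might infer that the table can only understate toxicity. The documents do not support that for the shift: step 4 shows it can move either way if a pre-dose repeat is dropped. Percentages can also move either way, because SAP 4.0 uses non-missing denominators and a subject with only unscheduled values would leave them.

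**Conclusion.** The point holds as an unresolved scope with a one-sided risk for the worst post-dose grade. Read literally, SAP 4.0 limits that grade to at most four draws and, with baseline fixed, can only lower it or leave it unchanged. Limiting the exclusion to by-visit summaries could give a different table, but only if some subject's unscheduled grade exceeds all of that subject's scheduled grades. How often that happens is unknown. Each such subject shifts a cell by 16.7 percentage points in a cohort of 6, or 4.2 points over 24 subjects.

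A reader might go further and infer that the plan hides laboratory toxicity or weakens dose escalation. The documents do not show this. Listings and adverse-event tables remain. The monitoring board reviews adverse events and laboratory values, with its data format left to a separate charter, and nothing links escalation to this shift table.

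Severity is minor to should-fix: the consequence is limited, but the table belongs to the primary objective and is easy to correct.

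**What to change.** - In SAP 4.0, replace the exclusion sentence with: *Unscheduled measurements will be excluded from by-visit descriptive summaries.* Keep the measurement-error exception and the listing of all unscheduled values.
- In SAP 6.7.1.4, add: *The worst post-baseline grade uses all post-dose laboratory values, scheduled and unscheduled, except values replaced because of measurement error; baseline is the last value before dosing, whether scheduled or unscheduled.* The baseline clause agrees with the definitions in Protocol 9.2 and SAP 4.0 and closes the question raised in step 4.

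If the sponsor does want scheduled draws only, SAP 6.7.1.4 and a table footnote should say so. SAP 9.0 should then record it, since Protocol 12.5.2 puts no such limit on the shift table.

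The cost is two sentences and minor programming. No new data are needed, because unscheduled results are already to be listed.

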## **5.0 ANALYSIS POPULATION**

The populations used for analysis will include intent-to-treat population, full analysis set, per protocol set and safety population. The primary objective endpoints analysis and safety endpoints will be performed based on safety population. Full analysis set and per protocol set will be used as the analysis population for secondary and exploratory efficacy endpoints. Baseline characteristics analysis will be performed on intent-to-treat population.

### **Intent-to-Treat Population**

The Intent-to-Treat population is defined as any subject who is enrolled into the study, whether or not he/she received study drug.

### **Full Analysis Set**

The full analysis set is defined as any subject who is enrolled into the study, received study drug, and has at least 1 efficacy evaluation after receiving study drug.

### **Per Protocol Set**

The per protocol set is defined as any subject who is enrolled into the study, received study drug as planned, has at least 1 efficacy evaluation after receiving study drug, completes the week 13 visit, and has no significant protocol violations. Significant protocol violation list will be documented in a separate file.

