6.5.2 Pain Medications

A summary of allowed pain medication by study phase is provided in [Appendix A](#). The following restrictions on pain medications are to be followed during the first 13 weeks post-dose and do not apply beyond the Week 13 visit.

1. Initiation of treatment or change in the dose regimen is disallowed for antidepressants, anticonvulsants, or any prescription or over the counter pain modulating drugs from screening to 13 weeks post-dose. If subjects are on a stable dose of any of the above medications for at least 4 weeks prior to screening, the same dose regimen should be continued through 13 weeks post-dose.
2. Initiation of treatment or dose escalation of muscle relaxants or sedatives/hypnotics is disallowed. A stable dose regimen if initiated at least 1 week prior to screening may be continued unchanged through 13 weeks post-dose. However, temporary use of a new muscle relaxant or sedative/hypnotic or dose increase of already used muscle relaxant or sedative/hypnotic will be allowed for treatment of a documented AE, for the duration of the event only. If clinically indicated, dose reduction or discontinuation of treatment is also permitted.
3. Epidural steroid injections/selective nerve root block/facet block are allowed if medically necessary within the first 13 weeks post-dose and beyond. However, the indication for the procedure (e.g., intractable lower back pain/worsening of lower back pain) must be documented as an AE (or SAE if it meets the SAE criteria defined in [Section 9.9.7](#)). Subjects who require a surgical intervention for treatment of disc herniation will be discontinued from the study.
4. Opioid and nonopioid analgesics (including topical analgesics) used for pain management on a stable dose at least 1 week prior to screening may be continued at the same or lower dose during the first 13 weeks post-dose. No dose escalation and no new opioid or nonopioid analgesics will be allowed except for acetaminophen. However, as described in [Section 6.5.1](#), temporary use of a new analgesic or dose increase of an already administered analgesic will be allowed to treat a documented AE, for the duration of the event only. Daily doses of all analgesics including rescue doses of acetaminophen will be recorded by the subjects in the provided diaries.

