6.6 Subject Withdrawal and Discontinuation

Subjects are free to discontinue the study at any time, for any reason, and without prejudice to further treatment. The investigator may remove a subject if, in the investigator's judgment, continued participation would pose unacceptable risk to the subject or to the integrity of the study data.

Subjects must discontinue from the study for any of the following reasons:

- The subject experiences an intercurrent illness that in the opinion of the investigator indicates continued participation in the study is not in the subject's best interest
- The subject is unable or unwilling to comply with the protocol
- The subject withdraws informed consent
- The subject is lost to follow-up
- The subject requires lumbar spine surgery
- A female subject tests positive for pregnancy

All procedures for early termination must be completed ([Section 11.13](#)). Subjects who are withdrawn prior to administration of study drug will be replaced to ensure a total of 6 evaluable subjects in each study cohort.

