11.12 End of Study Visit (24 Months/104 Weeks ±4 weeks)

- Review concomitant and prior medications
- MRI and X-ray
- Physical examination including measurement of weight without shoes
- Neurologic examination
- Vital signs (including BP, pulse, respiratory rate, and temperature)
- Review AEs

11.13 Early Termination Before Week 13

Same procedures as those outlined for Visit 6 (Week 13) in [Section 11.7](#).

11.14 Early Termination Between Week 13 and Month 24/Week 104

Same procedures as those outlined for the End of Study visit in [Section 11.12](#).

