### 6.2 Protocol Deviations

A protocol deviation is defined as any intentional or unintentional change to, or noncompliance with, the approved protocol procedures or requirements. Deviations may result from the action or inaction of the subject, investigator, or site staff. Examples of deviations include, but are not limited to:

- Failure to adhere to study exclusion and inclusion criteria.
- Failure to comply with dispensing or dosing requirements.
- Use of medications, food, drink, herbal remedies, or supplements that are specifically prohibited in the protocol.
- Missed or out-of-window visits.
- Drug dosing not administered within the time frame specified in the protocol.
- Failure to adhere to test requirements, including vital signs, laboratory tests, physical examinations, PK blood draws, medical history, etc. either tests not done, incorrect tests done, or not done within the time frame specified in the protocol.
- Procedural deviations such as incorrect storage of study drug, failure to update the Internal Consent Form (ICF) when new risks become known, failure to obtain Internal Review Board (IRB) approvals for the protocol and ICF revisions.

Protocol deviations will be identified by the project team prior to database lock. A summary of major protocol deviations will be provided by cohort. All protocol deviations will be listed. Intent-to-treat population will be used as an analysis population for this analysis.

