### **6.7.2 Analysis of Exploratory Efficacy Endpoints**

Exploratory efficacy endpoints analyses will be performed on the full analysis set and per protocol set and all analyses will be presented using descriptive statistics as mentioned in the [section 4](#). For all measures other than the daily pain, the baseline value is defined as the last assessment result collected prior to the first dose of study medication. For daily pain assessments, the baseline value is defined as the average of the results of 5 consecutive days prior to the first dose of study medication.

The following are the primary exploratory efficacy endpoints:

- Change from baseline in lower back pain or leg pain (numerical pain scale for each sub categories as mentioned below) at 6 and 13 weeks

- Leg average daily pain
- Leg worst daily pain
- Low back average daily pain
- Low back worst daily pain
- Current leg pain
- Current low back pain
- Number of subjects requiring:
  - Additional pain medication (and amounts) added to the subject's baseline pain regimen within the first 13 weeks post-dose
  - An epidural injection, a selective nerve root block, or a facet block after receiving study drug,
  - Surgical intervention for lumbar disc herniation
- Change from baseline in spinal flexion and tension signs (straight-leg raising or femoral stretch test) on the affected side at 6 and 13 weeks
- Change from baseline in ODI at 6 and 13 weeks
- Change from baseline in SF-12 at 6 and 13 weeks
- Change from baseline in the PGI-C at 6 and 13 weeks

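### The per-protocol count of disc surgeries before Week 13 is zero by construction, because surgery itself removes the subject from the Per Protocol Set

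*SAP*

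**What the plan says.** SAP 6.7.2 states: "Exploratory efficacy endpoints analyses will be performed on the full analysis set and per protocol set". SAP 4.0, 5.0 and 6.7 repeat the two-set rule, and no endpoint is exempted. Among the endpoints listed in 6.7.2 are counts of subjects requiring:

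- pain medication added to the "baseline pain regimen within the first 13 weeks post-dose";
- an epidural injection, nerve root block or facet block after dosing;
- "Surgical intervention for lumbar disc herniation", with no time limit.

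To enter the PPS (SAP 5.0; same definition in Protocol 12.3), a subject must have received drug as planned and have at least one post-dose efficacy evaluation. It must also hold that he or she "completes the week 13 visit, and has no significant protocol violations". The list of significant violations is kept in a separate file.

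Protocol 6.5.2, item 3, says: "Subjects who require a surgical intervention for treatment of disc herniation will be discontinued from the study". Protocol 6.6 puts the same event on the list of reasons for which a subject must leave: "The subject requires lumbar spine surgery". Protocol 11.13 provides a separate early-termination visit for those who leave before Week 13. It uses the Week 13 procedures.

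**The concern.** A per-protocol set is meant to select on how the protocol was followed. Here, for one endpoint, it selects on the outcome: the event being counted decides whether the subject is in the set in which it is counted. Before Week 13 the PPS surgery count cannot respond to the treatment or to the dose.

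This matters because the trial plans no hypothesis test, so the cohort tables are the efficacy evidence. With 6 subjects per cohort, a reader will set the FAS and PPS columns side by side. A row of zeros in the PPS looks like an observation when it is a consequence of the definition. The PPS denominator shrinks by the same subjects.

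**Working it through.** The documents give no surgery rate and no expected count, so there is no figure of the plan to reproduce. The only related number is the sample size, 4 cohorts × 6 = 24.

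**Step 1: membership.** Take a treated subject who needs disc surgery before Week 13.

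1. Protocol 6.5.2 and 6.6: the subject must be discontinued.
2. Protocol 11.13: the subject leaves through the early-termination visit, which is distinct from Visit 6 (Week 13).
3. SAP 5.0: the Week 13 visit is not completed, so the subject is not in the PPS.
4. The subject remains in the FAS, given at least one post-dose efficacy evaluation (pain is scored from 2 hours after injection), and in the Safety Population.

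Hence the number of PPS subjects with surgery before Week 13 is 0 with probability 1, at any true surgery rate.

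**Step 2: what one cohort would show.** If k of 6 subjects have surgery before Week 13 and nobody else is excluded, the FAS shows k/6 and the PPS shows 0/(6 − k):

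| k | FAS | PPS |
|---|---|---|
| 1 | 1/6 (16.7%) | 0/5 (0%) |
| 2 | 2/6 (33.3%) | 0/4 (0%) |
| 3 | 3/6 (50.0%) | 0/3 (0%) |

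For a count over the whole study, suppose two subjects have surgery before Week 13 and one after. The FAS shows 3/6 (50.0%). The PPS shows 1/(6 − 2) = 1/4 (25.0%). The PPS figure is no longer zero, but it still omits both early events.

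**Step 3: how often it would matter.** Let p be the surgery rate by Week 13. It is an assumption, shown over a range. Expected surgeries among 24 are 24p. The chance of at least one in a cohort of 6 is 1 − (1 − p)^6. If early surgery is the only reason for exclusion, the expected PPS size is 24(1 − p).

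| Assumed p | Expected in FAS (of 24) | At least one in a cohort of 6 | PPS count before Week 13 | Expected PPS size |
|---|---|---|---|---|
| 5% | 1.2 | 26.5% | 0 | 22.8 |
| 10% | 2.4 | 46.9% | 0 | 21.6 |
| 20% | 4.8 | 73.8% | 0 | 19.2 |
| 30% | 7.2 | 88.2% | 0 | 16.8 |
| 50% | 12.0 | 98.4% | 0 | 12.0 |

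A simulation of 24 subjects at 5%, 30% and 50% gave the same means (1.2, 7.2 and 12.0 surgeries in the FAS; 0.0 in the PPS).

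**Step 4: the other two counts.** Protocol 6.5.1 and 6.5.2 allow acetaminophen rescue, temporary analgesic changes to treat an adverse event, and medically necessary blocks. None of these is a violation in itself, so neither count is forced to zero. Two weaker links to the outcome remain. A subject who received a block or added medication and then had surgery before Week 13 leaves the PPS with those events. Also, SAP 6.2 gives as an example of a deviation "Use of medications, food, drink, herbal remedies, or supplements that are specifically prohibited in the protocol", so use of a disallowed analgesic would lower the PPS medication count if the separate file classes it as significant. That file is not among the documents.

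**The case against.** Four stronger readings are tempting, and the documents do not support them.

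- **That the PPS will show no surgery at all.** The surgery endpoint has no time limit and subjects are followed to Month 24. Surgery after a completed Week 13 visit is counted in the PPS. The structural zero stops at Week 13.
- **That the added-medication count is also empty by construction.** It is not, for the reasons in Step 4 of the working. Moreover, SAP 9.0 says the summary counting rescue medication was removed, while SAP 6.7.2 still describes one. Whether that count is planned at all must be settled first.
- **That the PPS is offered as confirmation of the FAS.** The SAP gives it no such role. All efficacy analyses are exploratory and descriptive in an uncontrolled study, and Protocol 5.1.2 rests escalation on the safety review by the data and safety monitoring board.
- **That Week 13 pain and disability summaries look better in the PPS because early surgeries are dropped.** SAP 4.0 summarises by nominal visit and SAP 7.0 imputes nothing, so a subject who left earlier has no Week 13 value in the FAS either. Only earlier visits, such as Week 6, could differ between the sets on this account.

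Two further objections bear on the narrower point. The early-termination visit borrows the Week 13 procedures, and the SAP does not say outright that it fails to count as completing Week 13. If it did count, the zero would not be guaranteed. The ordinary reading is that it does not, because the protocol lists the two visits separately. The second objection stands: surgery is visible elsewhere. It is in the FAS count, in the primary safety endpoint on discontinuations (SAP 6.7.1, Safety Population), in the adverse events of special interest and in disposition by cohort. Concomitant procedures are summarised on the intent-to-treat population (SAP 6.5). This limits the consequence but does not make the PPS count informative.

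**Conclusion.** Wrong as written, minor. On the ordinary reading of SAP 5.0 with Protocol 6.5.2 and 6.6, the PPS count of surgeries before Week 13 is zero at any true rate, and a whole-study PPS count leaves out every early surgery. In a cohort of 6, two early surgeries turn 2/6 into 0/4.

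The conclusion assumes that the mandatory discontinuation is applied and that an early-termination visit is not treated as completing Week 13. The surgery rates in the working are illustrative. They show how often the two columns would disagree, and the zero does not depend on them. The harm is a misleading table beside a sound one.

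**What to change.** In SAP 6.7.2, state that the counts of subjects requiring surgery, blocks or additional pain medication are presented for all treated subjects only (name either the FAS or the Safety Population) and not for the PPS. Record this in SAP 9.0 as a change. In the same edit, reconcile SAP 9.0 with SAP 6.7.2 on whether the rescue-medication count is still planned.

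Leave the PPS definition unchanged. It matches Protocol 12.3, and redefining it is not needed to remove this fault.

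The cost is one sentence, its entry in SAP 9.0 and fewer tables. Study conduct and data collection are unaffected.
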